1. STUDY OBJECTIVES

1.1 Primary Objectives

1.1.1 Aim 1

Aim 1 is to compare telecare collaborative pain management (TCM) versus integrated pain team (IPT) management for improving pain and reducing opioid use in VA patients on long-term moderate to high-dose opioids for chronic pain.

All participants will be randomized to one of two care management approaches: 1) TCM or 2) IPT. To assess improvement in pain and reduction in opioid use, we will compare TCM versus IPT groups on three main outcomes. First, the primary outcome is pain response, defined as a 30% improvement in Brief Pain Inventory (BPI) total score from baseline to the final study outcome assessment at 12 months. Our second main outcome is opioid daily dose reduction of 50% from baseline to 12 months, based on VA pharmacy dispensing data. The main composite outcome is the proportion with both a pain response and opioid dose reduction, representing dual improvements in pain and regimen safety.

1.1.2 Aim 2

Aim 2 is to compare standard versus expanded taper options for improving pain and reducing opioid use among patients on high-dose opioid therapy at baseline.

Participants in the high-dose therapy subgroup will be randomized to receive one of two opioid taper arms: a) standard options or b) expanded options, which includes the additional option of buprenorphine rotation. To assess the primary outcome of pain severity, we will compare standard versus expanded options groups on mean BPI total scores. Between-group differences in opioid daily dose and the composite pain response and opioid dose reduction outcome will also be examined. We hypothesize that offering the option of buprenorphine rotation will improve BPI scores and reduce opioid daily dose.

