Participants are not considered enrolled until the signed written informed consent and HIPPA authorization forms are received. If the signed consent and HIPAA authorization forms are not received within 14 days, study personnel will follow-up with the patient by telephone to determine interest in participation and troubleshoot problems with the forms or mail. Replacement copies will be provided, if needed. If the signed consent/HIPAA forms are received after 45 days, baseline outcome measures must be repeated prior to randomization. If study personnel do not succeed in contacting the patient by 45 days after the enrollment visit, no additional attempts will be made.

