4.3.9 Randomization

After obtaining the written informed consent document (either in person or upon receipt of the original mailed copy) and completing the baseline interview, the local site coordinator/research assistant will initiate randomization using the study application randomization form. The randomization code will not be visible to personnel conducting randomization and can be completed only once per study ID, preventing study personnel from influencing treatment allocation. This process will simultaneously inform the coordinator and participant of the primary study arm assignment. To prevent patients from feeling pressured to taper opioids, the taper option assignment will be revealed only when participants agree to discuss options for opioid dose reduction. Regardless of whether the taper intervention is delivered, participants will be evaluated in their assigned arm.

Patients will be randomized within site and opioid dose (i.e., moderate or high) categories, in permuted blocks of size 4 or 8, to balance the proportions of participants with moderate-dose and high-dose opioid therapy in the intervention arms. Those in the moderate-dose group will be randomly assigned, with equal likelihood, to intervention arms. Those in the high-dose group will be randomly assigned, with equal likelihood, to intervention and tapering strategy combinations.

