4.3.10 Masking

Participants will not be masked to treatment arm assignment due to the complexity of the intervention strategies. Local site treatment teams and local site study personnel will also be unmasked. To reduce risk of biased outcome ascertainment, all personnel conducting outcome assessments will be masked to treatment arm assignment.

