6.2 Patient-reported measures

Patient-reported measures, including outcomes and covariates, will be collected by interview at baseline and at 3, 6, 9, and 12 months. The baseline interview will be conducted by the local site study coordinator or research assistant after the patient provides verbal informed consent and before randomization. Follow-up outcome assessments will be conducted as telephone interviews by coordinating center research personnel who are masked to treatment arm assignment. Visual aids will be mailed to participants in advance so they can follow along with the interviews. If participants are unable to complete 6 or 12-month telephone interviews, they will be offered the alternative of completing mailed paper questionnaires. Participant responses will be recorded on machine-readable paper questionnaire forms, which will be subsequently double-scanned into an electronic database. Interviews are completed with the most critical measures first, to prevent missing core outcome data in case of interruption.

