6.2.1 Timing and duration of assessment interviews

Full-length assessment interviews will be conducted at baseline, 6 months, and 12 months. The duration of assessment interviews will be approximately 60 minutes at baseline and 45 minutes at 6 and 12 months. A small participant payment (\$50 each) will be provided after each of these interviews. A nominal token of appreciation (e.g., jar opener with study logo) will be sent to participants before the 12-month interview.

Abbreviated assessment interviews addressing core outcome measures will be conducted at 3 and 9 months. The duration of these abbreviated interviews will be approximately 15-20 minutes. A small participant payment (\$25 each) will be provided after each abbreviated interview.

Timing of follow-up assessment interviews will be based on the date of the baseline interview. Follow-up assessments may be completed up to 30 days early when extenuating circumstances (e.g., planned travel or move) suggest that data may be otherwise lost. 3 and 9 month assessments may be completed up to 30 days late. 6 and 12 month assessments may be completed up to 60 days late. Data from assessments completed outside of these time windows will not be included in primary analyses.

If the first intervention visit is delayed >30 days after baseline assessment date, participants will be asked to repeat core baseline measures (administered by masked assessors), prior to the first intervention visit. A small participant payment (\$25 each) will be provided after the abbreviated, repeat baseline interview.

At the end of the 12-month interview, the assessor will ask for permission to re-contact the Veteran, either for a qualitative interview (described below in 6.4.1) or other future interviews; participants will be reminded these future interview(s) are voluntary.

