7.3 Statistical Analysis of Primary Aim

We will use all follow-up data in a repeated-measures logistic regression modeling 30% reduction from baseline in BPI scores at the quarterly follow-up assessments. The regression model will use assigned intervention, assessment point, and their interaction as explanatory measures. Assessment points will be incorporated as random effects, with non-zero means and an unstructured covariance, to model potential correlation among outcomes for individuals. Our primary assessment of intervention effects will examine differences in the log odds of attaining a 30% reduction in BPI at the 12-month assessment using a two-sided Wald test (0.05 significance level), together with the corresponding model-based odds ratio point and confidence interval estimates.

To assess the sensitivity of these initial analyses to response bias, we will fit a series of weighted selection model analyses. Each analysis will use an EM algorithm to estimate weights to assign to potential values of the missing outcomes for use in logistic regression. The regression will model the log odds of a reduction in BPI at 12 months using the assigned intervention and relevant baseline measures as predictors. The EM algorithm will jointly use a logistic model for observation of the 12-month outcome to iteratively update the weight estimates. These latter logistic models will be varied to use different combinations of the following variables—12-month outcome, intervention, observation and value of the outcome at prior assessments, and baseline covariates together with pain measurements and services utilization over the follow-up period—as predictors to consider different potential missing at

random and missing not at random mechanisms generating the missing data. The approach outlined above will also be used to examine differences in reduction in opioid use at 12 months, the combination of pain reduction and opioid use reduction, and the BPI severity and interference subscales.

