7.4 Pre-Specified Subgroup Analyses

We will examine variation in the intervention effects on the change in BPI within clinical subgroups defined by presence or absence at baseline of the subgroup status/conditions described above. For each subgroup measure, we will fit a repeated-measures linear regression modelling change from baseline in BPI at the quarterly follow-up assessments using assigned intervention, assessment point, subgroup indicator and all interactions between these three measures together with baseline BPI score and its interaction with assessment point as explanatory measures. Assessment points will be incorporated as random effects, with an unstructured covariance, to model potential correlation among outcomes for individuals. Our primary assessment of an interaction between intervention and the subgroup measure will use the model-based two-sided Wald test for an interaction at the 12-month assessment, using a 0.005 significance level. Weighted selection model analyses similar to those described above will examine sensitivity of 12-month results to response biases.

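### Does the repeat baseline interview after a late first visit leave the reference score for the BPI response endpoint open?

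*Combined protocol and SAP*

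**What the plan says.** Section 6.2 has local site staff conduct the baseline interview "after the patient provides verbal informed consent and before randomization". Section 6.2.1 dates the follow-up assessments from that interview. It then adds that, if the first intervention visit comes more than 30 days after the baseline assessment date, "participants will be asked to repeat core baseline measures (administered by masked assessors), prior to the first intervention visit". The revision history shows that this rule came in with version 11 (May 2020).

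Sections 5.3.2 and 5.4.2 place the first visit after randomisation in both arms. Of randomisation, section 4.3.9 says: "This process will simultaneously inform the coordinator and participant of the primary study arm assignment". Section 4.3.10 adds: "Participants will not be masked to treatment arm assignment due to the complexity of the intervention strategies".

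A separate rule in section 4.3.8 covers signed consent forms that arrive after 45 days. In that case "baseline outcome measures must be repeated prior to randomization".

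The endpoint and models refer to baseline without further definition. Section 1.1.1 has pain response "defined as a 30% improvement in Brief Pain Inventory (BPI) total score from baseline to the final study outcome assessment" at 12 months. Section 7.3 fits "a repeated-measures logistic regression modeling 30% reduction from baseline in BPI scores at the quarterly follow-up assessments". The subgroup models in section 7.4 model change in BPI "together with baseline BPI score and its interaction with assessment point as explanatory measures".

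**The concern.** The primary endpoint is a ratio to baseline, so the reference score sets each participant's responder cut-off. If the repeat replaced the original, some participants would be judged against a score given after allocation by someone who knows the arm. Those participants would also be a subset defined by an event after randomisation, the late first visit. Masked assessors limit interviewer bias, but the participant supplies the pain rating.

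The late-consent rule in section 4.3.8 confines its repeat to the time before randomisation. The late-visit rule in section 6.2.1 has no such limit. Delay could plausibly differ by arm: the first IPT visit needs a medical provider and a mental health therapist, while the first TCM visit needs one pharmacist. The pain response outcome, the composite that contains it and the models that adjust for baseline BPI could all be affected, and the choice of score could in principle be made after the data are seen.

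**Working it through.** **Which score the text points to**

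- Section 6.2 identifies the baseline interview as the one done by local staff before randomisation.
- Section 6.2.1 counts the 30-day delay from the baseline assessment date. This can only be the original interview, because the repeat is triggered by that delay.
- The same section dates follow-up from the baseline interview and describes the later contact separately, as an abbreviated repeat with its own assessors and payment.
- No section says that repeat scores enter an endpoint or a covariate.
- Section 4.3.8 requires a repeat but does not say that it supersedes the first score. As it precedes randomisation, either score would be a valid reference.

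The documents therefore lean towards the pre-randomisation score without saying so outright.

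**Which outcomes could be touched**

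- BPI is very probably among the repeated core measures. The 3- and 9-month interviews are limited to core outcomes, and section 7.3 needs BPI at those visits.
- Opioid dose outcomes use pharmacy dispensing averaged over 90 days (section 6.3.2), so no interview affects them.
- The taper assignment is disclosed only when a participant agrees to discuss dose reduction (section 4.3.9). Before the first intervention visit, participants know TCM or IPT only. The issue is mainly one for Aim 1.

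**The plan's own figure**

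Sections 7.1 and 7.1.1 give 970 enrolled, 776 effective (388 per arm), 50% against 60% response and two-sided alpha 0.05. A two-proportion calculation gives 80.1% power, which agrees with the stated 80%. The choice of reference does not alter the sample size.

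**Effect on the cut-off**

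Cut-off = 0.7 × reference. A reference of 6.5 gives 0.7 × 6.5 = 4.55, and 6.0 gives 0.7 × 6.0 = 4.20. A full-unit fall moves the cut-off by 0.70.

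**Effect on the arm difference, with no true effect**

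The simulation takes the BPI SD of 2 (section 7.1.2) and 50% response (section 7.1.1) from the plan. It assumes a mean baseline of 6.5, reliability of 0.6 to 0.9 and an SD of true change of 1.0 or 1.5. A participant responds if the 12-month score is at most 0.7 × reference. There are 1,200,000 simulated participants per arm, and the Monte Carlo standard error is about 0.07 points. All delay rates and shifts are assumed.

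| Reference | Delay by arm | Shift in repeat score | False difference (points) |
|---|---|---|---|
| Original | any | any | -0.1 to +0.1 (nil within simulation error) |
| Repeat | 30% vs 15% | none | -0.1 to +0.2 (zero in expectation) |
| Repeat | 30% in both | -0.5 in both | -0.1 to +0.1 |
| Repeat | 10% vs 5% | -0.3 to -1.0 in both | 0.1 to 0.9 |
| Repeat | 10% in both | -0.5 vs +0.5 | 1.3 to 1.9 |
| Repeat (extreme) | 30% vs 15% | -0.3 to -1.0 in both | 0.5 to 3.0 |
| Repeat (extreme) | 50% vs 20% | -0.3 to -1.0 in both | 1.2 to 5.7 |
| Repeat (extreme) | 30% in both | -0.5 vs +0.5 | 3.7 to 5.8 |

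A second simulation assumed correlations of 0.7 between original and repeat and 0.5 with month 12. Swapping the baseline changed responder status in about 19% of repeated participants, yet the arm difference stayed at about zero when there was no arm-related shift. With 10% repeated in each arm and a +0.5 shift in IPT only, the false difference was 0.7 points.

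**Scale**

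The standard error of the arm difference is √(2 × 0.5 × 0.5 / 388) = 0.0359, or about 3.6 points. The 10% delay scenarios amount to 0.1 / 3.59 = 0.03 up to 1.9 / 3.59 = 0.53 standard errors. At 0.53, the two-sided type I error is P(Z > 1.43) + P(Z < -2.49) = 0.076 + 0.006, about 8.3%. At 0.03 it is 5.0%.

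**The case for a change.** The strongest case for a change is that the text never rules replacement out. The protocol calls the later contact a baseline interview of a kind. Requiring masked assessors makes sense only if the contact is expected after allocation. If the original score always stands, the plan gives the repeat no stated analytic use. Two competent analysts might differ, and a sentence would settle it at almost no cost.

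Much of this stands. The silence is real, BPI is very probably in the repeated set, and most repeats would come from participants who know their TCM or IPT arm. The intention-to-treat commitment in section 7.2 does not settle the matter, because it governs the arm in which people are analysed and not the score they are compared with.

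The step from silence to a wrong result does not stand. To use the repeat, an analyst would have to set aside the interview that section 6.2 designates as baseline and adopt a post-randomisation reference that no section asks for. The repeat can still describe pain at the start of care, so its existence does not imply substitution.

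The larger biases also need conditions that the documents do not suggest. First visits are to be booked promptly after randomisation. The rule began only with version 11, and version 12 then added telephone visits. Time spent waiting for mailed consent forms uses up part of the 30 days before allocation, so that part of the delay cannot be caused by the arm.

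Keeping the original has a price. The reference is older for delayed participants, and a 12-month assessment done on schedule then follows less than 11 months of intervention (12 months less more than 30 days). That is a fair trade for a reference that allocation cannot influence.

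**Conclusion.** No change to the plan is needed. This is a detail left unwritten, and the surrounding text leads an analyst to fill it correctly with the pre-randomisation BPI score, for which there is no bias. A clarifying sentence would do no harm, but following the plan as written has not been shown to give a wrong answer.

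A false arm difference needs both replacement by a post-randomisation repeat and scores that shift, with the delay or the shift differing between arms. If those conditions held with at most 10% delayed, the difference would be 0.1 to 1.9 points, about 0.03 to 0.53 standard errors, against the 10 points the trial is designed to detect. The 30% to 50% delay scenarios, reaching 5.8 points, are extremes.

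These sizes rest on assumed delay rates, shifts, mean baseline, reliability and spread of true change. Only the BPI SD of 2 and the 50% response rate come from the plan. A markedly higher delay rate, combined with actual use of the repeat as the reference, would make the matter more serious.

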6.2.2 Alternative patient-reported assessment procedures

If assessment burden becomes a problem for participants at any point during the study, the option of completing a minimum assessment composed of core outcome measures will be offered. If participants are unable to complete interviews by telephone, a self-complete machine-readable paper questionnaire will be mailed. Participant payments will be provided as described above.

6.2.3 Description of patient-reported measures

Consistent with guidelines for outcome assessment in pain clinical trials, we will assess multiple domains, including pain intensity, function, and symptoms and adverse events, using validated patient-reported measures. Patient-reported outcome domains and data collection schedule are presented in Table 2.

Table 2: Patient-reported outcome assessment schedule

Measure	Schedule (month)				
	0	3	6	9	12
Pain, pain characteristics	X	X	X	X	X
Health related quality of life	X	X	X	X	X
Functioning	X	X	X	X	X
Adverse effects	X	X	X	X	X
Fatigue/sleep	X		X		X
Mood (e.g., anxiety, depression, PTSD)	X		X		X
Substance use	X				X
Predictors/explanatory variables	X		X		X
Use of health care services/self-care practices	X		X		X
COVID-19 questions	X	X	X	X	X

6.3 Administrative Data

6.3.1 Data sources

National VA datasets and the environment for analyzing them are provided by VA Informatics and Computing Infrastructure (VINCI). A VINCI project workspace will be used to access data, construct covariates, and perform primary and secondary analyses.

We will use administrative data to determine eligibility, covariates and outcomes, including the following:

- Patient eligibility criteria from outpatient pharmacy and inpatient and outpatient data domains
- Relationships of patients and primary care providers from PCMM domain
- Patient demographics from patient data domain
- Patients distance and drive time from VA facilities from geographic access data sets created by the planning services and support group
- Physical and mental health diagnoses from inpatient and outpatient data domains
- Prescriptions and drug dispensing from outpatient pharmacy domain
- Pain treatment variables from outpatient and lab chemistry data; outpatient pharmacy data; and outpatient, procedure code, and fee basis data domains
- Hospitalizations, ED visits, and SUD treatment admissions from inpatient, outpatient, procedure code, and fee basis data domains
- COVID-19 test results

6.3.2 Opioid dispensing data

Opioid dose outcomes and medication covariates will be assessed using VA outpatient pharmacy dispensing data. Opioid daily dose at any given time will be calculated as the mean dose over the prior 90 days, so the main opioid dose outcome will therefore be an average dose over the final 90 days of the study intervention period. To provide information about dose after the intervention is complete, our final dose assessment time-point will be three months after the end of the study. Established conversion tables will be used to calculate morphine-equivalent (ME) mg.

6.3.3 Pain treatment data

Receipt of pain-related services outside of intervention visits will be estimated by capturing specialty, rehabilitation, and mental health visits. Complementary therapies are not all well captured in VA databases, but therapies with specific codes (e.g., acupuncture) will be assessed. Other complementary services may be variably recorded under general codes; for example, yoga could be coded as a recreational therapy visit. To maximize our capture of VA complementary therapy service delivery and validity of these data across sites, local study personnel at each site will be asked to inventory local complementary therapy availability and clinical coding practices on an annual basis; these inventories will be reviewed by the coordinating center data and statistical team and considered in administrative data extraction and cleaning protocols.

6.3.4 Intervention treatment data

Data will be collected on intervention visits to describe the care provided, as well as fidelity to the intervention arms (see 5.8). Intervention clinic visit notes will be used to count the number of intervention visits (face-to-face, video and telephone) in both arms over the study period. Structured notes will be designed to generate data objects that can later be captured from administrative data to describe intervention processes.

